## Appendix 10 CLASI

Select the score in each anatomical location that describes the most severely affected cutaneous lupus-associated lesion

[figure not shown]
activity			damage		
Anatomical Location	Erythema	Scale/ Hypertrophy	Dyspigmentation	Scarring/ Atrophy/ Panniculitis	Anatomical Location
	0- absent 1- pink; faint erythema 2- red; 3- dark red; purple/violaceous/ crusted/ hemorrhagic	0-absent; 1-scale 2-verrucous/ hypertrophic	0-absent, 1-dyspigmentation	0 – absent 1 – scarring 2 – severely atrophic scarring or panniculitis	
Scalp				See below	Scalp
Ears					Ears
Nose (incl. malar area)					Nose (incl. malar area)
Rest of the face					Rest of the face
V-area neck (frontal)					V-area neck (frontal)
Post. Neck &/or shoulders					Post. Neck &/or shoulders
Chest					Chest
Abdomen					Abdomen
Back, buttocks					Back, buttocks
Arms					Arms
Hands					Hands
Legs					Legs
Feet					Feet

## Mucous membrane

## Dyspigmentation

Mucous membrane lesions (examine if patient confirms involvement)		Report duration of dyspigmentation after active lesions have resolved (verbal report by patient – tick appropriate box)
0-absent		 Dyspigmentation usually lasts less than 12 months (dyspigmentation score above remains)
1-lesion or ulceration		 Dyspigmentation usually lasts at least 12 months (dyspigmentation score is doubled)

## Alopecia

Recent Hair loss (within the last 30 days / as reported by patient)		NB: if scarring and non-scarring aspects seem to coexist in one lesion, please score both
1-Yes 0-No		

Divide the scalp into four quadrants as shown. The dividing line between right and left is the midline. The dividing line between frontal and occipital is the line connecting the highest points of the ear lobe. A quadrant is considered affected if there is a lesion within the quadrant.
		

Alopecia (clinically not obviously scarred)
 
0-absent 1-diffuse; non-inflammatory 2-focal or patchy in one quadrant; 3-focal or patchy in more than one quadrant
		
Scarring of the scalp (judged clinically)
 
0-absent 3-in one quadrant 4-two quadrants 5-three quadrants 6-affects the whole skull

### Total Activity Score

(For the activity score please add up the scores of the left side i.e. for Erythema, Scale/Hypertrophy, Mucous membrane involvement and Alopecia)

1

### Total Damage Score

(For the damage score, please add up the scores of the right side, i.e. for Dyspigmentation, Scarring/Atrophy/Panniculitis and Scarring

\_\_\_\_\_

Confidential

## Appendix 11 Tender/swollen joints count

Assessment date:

/  /   /   /   /

Time:

:  :

Joint Position					Reason Not Evaluable
Shoulder					
Left	 None	 Tender	 Swollen	 Not Evaluable	
Right	 None	 Tender	 Swollen	 Not Evaluable	
Elbow					
Left	 None	 Tender	 Swollen	 Not Evaluable	
Right	 None	 Tender	 Swollen	 Not Evaluable	
Wrist					
Left	 None	 Tender	 Swollen	 Not Evaluable	
Right	 None	 Tender	 Swollen	 Not Evaluable	
Metacarpophalangeal (MCP) I					
Left	 None	 Tender	 Swollen	 Not Evaluable	
Right	 None	 Tender	 Swollen	 Not Evaluable	
Metacarpophalangeal (MCP) II					
Left	 None	 Tender	 Swollen	 Not Evaluable	
Right	 None	 Tender	 Swollen	 Not Evaluable	
Metacarpophalangeal (MCP) III					
Left	 None	 Tender	 Swollen	 Not Evaluable	
Right	 None	 Tender	 Swollen	 Not Evaluable	
Metacarpophalangeal (MCP) IV					
Left	 None	 Tender	 Swollen	 Not Evaluable	
Right	 None	 Tender	 Swollen	 Not Evaluable	

Confidential

Joint Position					Reason Not Evaluable
Metacarpophalangeal (MCP) V					
Left	 None	 Tender	 Swollen	 Not Evaluable	
Right	 None	 Tender	 Swollen	 Not Evaluable	
Finger Proximal Interphalangeal (Finger PIP) I					
Left	 None	 Tender	 Swollen	 Not Evaluable	
Right	 None	 Tender	 Swollen	 Not Evaluable	
Finger Proximal Interphalangeal (Finger PIP) II					
Left	 None	 Tender	 Swollen	 Not Evaluable	
Right	 None	 Tender	 Swollen	 Not Evaluable	
Finger Proximal Interphalangeal (Finger PIP) III					
Left	 None	 Tender	 Swollen	 Not Evaluable	
Right	 None	 Tender	 Swollen	 Not Evaluable	
Finger Proximal Interphalangeal (Finger PIP) IV					
Left	 None	 Tender	 Swollen	 Not Evaluable	
Right	 None	 Tender	 Swollen	 Not Evaluable	
Finger Proximal Interphalangeal (Finger PIP) V					
Left	 None	 Tender	 Swollen	 Not Evaluable	
Right	 None	 Tender	 Swollen	 Not Evaluable	
Knee					
Left	 None	 Tender	 Swollen	 Not Evaluable	
Right	 None	 Tender	 Swollen	 Not Evaluable	

Total number of tender joints:

Total number of swollen joints:

Total number of tender and swollen joints:

The actual assessment to be used will prevail

## Appendix 12 Conversion table from glucocorticoids to Prednisone

Glucocorticoid	Approximate equivalent dose (mg)	Conversion factor to Prednisone	Half - life (hs)
Cortisone	25	0.2	<12 (short)
Hydrocortisone	20	0.25	<12 (short)
Deflazacort	7.5	0.67	<12 (short)
Prednisolone	5	1	12–36 (medium)
Prednisone	5	1	12–36 (medium)
Methylprednisolone	4	1.25	12–36 (medium)
Triamcinolone	4	1.25	12–36 (medium)
Betamethasone	0.75	6.67	36–72 (long)
Dexamethasone	0.75	6.67	36–72 (long)

Conversion: any glucocorticoid x Conversion factor to Prednisone = Prednisone dose

Example: Triamcinolone 8 mg x 1.25 = Prednisone 10 mg

Reference: Goodman & Gilman's The Pharmacological Basis of Therapeutics (2023), chapter 50, page 1013

### Clarifications

- These dose relationships only apply to oral or IV administration. Glucocorticoid potencies may differ greatly following intramuscular or intra-articular administration.
  - Methylprednisolone (MEDROL) → oral
  - Methylprednisolone Succinate (SOLU-MEDROL) → IV (FDA label mentions the same conversion factor than methylprednisolone)
  - Methylprednisolone Acetate (DEPO-MEDROL) → IM, intra-articular or intra-lesional (FDA label mentions the same conversion factor than methylprednisolone)
- Fludrocortisone, even though is a glucocorticoid, it is used for its mineralocorticoid activity, the anti-inflammatory activity is negligible at normal therapeutic doses (1/10 that of hydrocortisone)

## **Appendix 13 Notable abnormalities for ECG, BP, and laboratory variables**

### **Notable abnormalities for ECG and BP**

Notable abnormalities for ECG and BP that are related to the potential effects of cenerimod will address the following variables:

- Morphological ECG findings (defined as any abnormal finding not present prior to start of treatment)
- HR outliers (bpm), based on ECG
- PR interval (ms)
- QT/QTc interval (ms), based on Bazett's or Fridericia's formula
- BP (mmHg)

The definition of the abnormal values to be reported will be described in the SAP.

### **Laboratory abnormalities**

Laboratory values below or above the normal range will be graded at three levels (H, HH, HHH for values above normal range and L, LL, LLL for values below the normal range) where L stands for “low”, H for “high”.

The term “marked abnormality” describes laboratory values above or below the thresholds, with grading of abnormalities at two levels: LL/HH and LLL/HHH. These thresholds have been defined by the sponsor in order to flag and/or communicate abnormal laboratory results from the central laboratory to the investigators, and for the purpose of standardized data analysis and reporting by the sponsor. The definitions of marked abnormal values are based mainly on the Common Terminology Criteria for Adverse Events grading system (2017 v5.0) and, in specific cases (e.g., lymphocyte levels), are adjusted based on the known PD effect of the study treatments (e.g., LLL threshold for lymphocytes) [CTCAE 2017].

The term ALERT here corresponds to the protocol-defined test result threshold requiring action from the investigator as described in the protocol (e.g., repeat the test, interrupt or discontinue the study treatment) and should not be confused with the term “call alert” used by the central laboratory for laboratory results which will be communicated to the investigator. Not all ALERTs listed in this table will be “call alerts” from the central laboratory and vice-versa.

PLEASE NOTE: Thresholds for abnormality of level L or H are not provided in this appendix but will be provided in the laboratory manual.

Parameter	LL	LLL	HH	HHH
Hemoglobin	< 100 g/L (< 10 g/dL; < 6.2 mmol/L)	< 80 g/L (< 8 g/dL; < 4.9 mmol/L)	Increase in > 20 g/L above ULN or above baseline (if baseline is above ULN)	Increase in > 40 g/L above ULN or above baseline (if baseline is above ULN)
MCH	n/a	n/a	n/a	n/a
MCV	n/a	n/a	n/a	n/a
Hematocrit	< 28% (female) < 32% (male)	< 20%	> 60% (male) > 55% (female)	> 65%
Platelet count	< 75 × 10 e9/L (< 75,000/mm  )	< 50.0 × 10 e9/L (< 50,000/mm  )	> 600 × 10 e9/L	> 999 × 10 e9/L
RBC count	ND	ND	ND	ND
WBC (leukocytes) total count	ND	< 1.9 × 10 e9/L	> 20.0 × 10 e9/L (> 20,000/mm  )	CTCAE (grade 3) > 100.0 × 10 e9/L (> 100,000/mm  )
Lymphocyte total	ND	< 0.2 × 10 e9/L (< 200/mm  ) ALERT* < 0.2 × 10 e9/L (< 200/mm  )	> 4.0 × 10 e9/L (> 4000/mm  )	≥ 8 × 10 e9/L (> 8000/mm  )
Neutrophils total	< 1.5 × 10 e9/L (< 1500/mm  )	< 1.0 × 10 e9/L (< 1000/mm  )	ND	ND
Eosinophils total	ND	ND	> 5.0 × 10 e9/L or > 5% (> 5000 cells/mm  )	ND
Monocytes total	ND	ND	ND	ND
Basophils total	ND	ND	ND	ND
Polymorphonuclear leucocyte/Band cells	ND	ND	> 90%	> 95%
AST	ND	ND	≥ 3 ULN ALERT ≥ 3 ULN	≥ 5 ULN ALERT ≥ 5 ULN ≥ 8 ULN
ALT	ND	ND	≥ 3 ULN ALERT ≥ 3 ULN	≥ 5 ULN ALERT ≥ 5 ULN ≥ 8 ULN
GGT	ND	ND	≥ 2 ULN	≥ 5 ULN
Total bilirubin	ND	ND	≥ 2 ULN ALERT ≥ 2 ULN combined with	≥ 5 ULN

Parameter	LL	LLL	HH	HHH
			ALT or AST ≥ 3 ULN	
Alkaline Phosphatase	ND	ND	> 2.5 ULN	> 5 ULN
INR	ND	ND	≥ 1.5** or ≥ 1.5 times above baseline if on anticoagulation ALERT ≥ 1.5 combined with ALT or AST ≥ 3 ULN	≥ 2.5** or ≥ 2.5 times above baseline if on anticoagulation
aPTT	ND	ND	> 1.5–2.5 × ULN	> 2.5 × ULN
Lactate dehydrogenase	ND	ND	ND	ND
Creatinine	ND	ND	> 1.5 ULN or > 1.5 × baseline	> 3 ULN or > 3 × baseline
Creatinine Clearance (eGFR)	<60 ml/min/1.73m 	< 30 ml/min/1.73m 	ND	ND
Urea	ND	ND	> 2.5 ULN	> 5 ULN
Uric acid	ND	ND	> 590 µmol/L (> 10 mg/dL)	> 720 µmol/L (> 12 mg/dL)
Proteinuria	ND	ND	≥ 1.0 g/24 h 2+ and 3+ proteinuria	≥ 3.5 g/24 h 4+ proteinuria
Protein/creatinine ratio	ND	ND	> 100 mg/mmol***	> 300 mg/mmol***
Albumin	< 30 (g/L)	< 20 (g/L)	ND	ND
Protein total	ND	ND	ND	ND
Glucose (non-diabetic Fasting)	< 3.0 (mmol/L) (< 55 mg/dL)	< 2.2 (mmol/L) (< 40 mg/dL)	> 8.9 (mmol/L) (> 160 mg/dL)	> 13.9 (mmol/L) (> 250 mg/dL)
Potassium	< 3.2 (mmol/L)	< 3.0 (mmol/L)	> 5.5 (mmol/L)	> 6.0 (mmol/L)
Sodium	ND	< 130 (mmol/L) (< 130 mEq/L)	> 150 (mmol/L) (> 150 mEq/L)	> 155 (mmol/L) (> 155 mEq/L)
Calcium (corrected for albumin)	< 2.0 (mmol/L) (< 8.0 mg/dL)	< 1.75 (mmol/L) (< 7.0 mg/dL)	> 2.9 (mmol/L) (> 11.5 mg/dL)	> 3.1 (mmol/L) (> 12.5 mg/dL)
Chloride	ND	ND	ND	ND
Triglyceride	ND	ND	> 3.42 (mmol/L)	> 11.4 (mmol/L)
Cholesterol	ND	ND	> 7.75 (mmol/L)	> 12.92 (mmol/L)
Creatin (phospho) kinase (CK, CPK)	ND	ND	> 5 × ULN	> 10 × ULN
IgG	Na	ND	ND	ND
IgM	ND	ND	ND	ND

Parameter	LL	LLL	HH	HHH
IgA	ND	ND	ND	ND
ANA	ND	ND	ND	ND
Anti-dsDNA	ND	ND	ND	ND
C3	ND	ND	ND	ND
C4	ND	ND	ND	ND
Anti-Sm	ND	ND	ND	ND
Anti-cardiolipin IgA	ND	ND	ND	ND
Anti-cardiolipin IgG	ND	ND	ND	ND
Anti-cardiolipin IgM	ND	ND	ND	ND
Serum pregnancy test	ND	ND	ND	Positive ALERT: Positive

GENERAL note: this table displays safety alerts for possible drug induced liver disease (DILI), lymphocytopenia as per protocol and serum pregnancy test. Additional alerts may be applicable, details are described in a respective section of laboratory manual.

\*The ALERT will provide the exact lymphocyte count. In addition, if lymphocyte count < 500 cells/ $\mu$ l at FSV, an ALERT will be sent.

\*\* HH and HHH based on CTCAE 2017 v5.0 [CTCAE 2017]. However, an ALERT will be sent when INR  $\geq$  1.5 based on the guidance for monitoring liver test abnormalities from the FDA [FDA 2009].

\*\*\* Source for protein/creatinine ratio thresholds: [ukkidney.org].

ALT = alanine aminotransferase; ANA = antinuclear antibodies; anti-dsDNA = anti-double-stranded deoxyribonucleic acid; anti-Sm = anti-Smith; aPTT = activated partial thromboplastin time; AST = aspartate aminotransferase; CTCAE = Common Terminology Criteria for Adverse Events; eGFR = estimated glomerular filtration rate; FDA = Food and Drug Administration; FSV = Final Study Visit; GGT- gamma glutamyl transferase; Ig = immunoglobulin; INR = international normalized ratio; LLN = lower limit of normal; MCH = mean corpuscular hemoglobin; MCHC = Mean corpuscular hemoglobin concentration; MCV = mean corpuscular volume; ND = not defined; RBC = red blood cell; ULN = upper limit of normal; WBC = white blood cell.

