**Table 5      Objectives and endpoints**

Objectives	Endpoints
To evaluate the safety and tolerability of cenerimod 4 mg in Chinese participants	

• Occurrence of TEAEs, SAEs and AESIs up to FSV.

• Occurrence of AEs leading to permanent discontinuation of study treatment.

• Changes in vital signs (SBP, DBP) and body weight from baseline to each post-baseline assessment.

• Changes in hourly 12-lead ECG variables (HR and the intervals: QTcB, and QTcF) and in SBP/DBP assessments at Day 1 cardiac monitoring.

Objectives	Endpoints
	

Changes in 12-lead ECG variables (HR and the intervals: PR, QRS, QTcB, and QTcF) from baseline to each post-baseline assessment.

Treatment-emergent medically relevant ECG abnormalities from baseline to each post-baseline assessment.

Changes in laboratory variables (hematology, blood chemistry, and urinalysis) from baseline to each post-baseline assessment.

Treatment-emergent marked laboratory abnormalities from baseline to all assessed time points.

To evaluate the PK of cenerimod 4 mg in Chinese participants.	
PK endpoints
 

Cenerimod plasma concentrations at all scheduled time points (see Table 2).

The plasma PK parameters of 4 mg cenerimod will be derived by non-compartmental analysis of the plasma concentration-time profiles and calculated based on the actual PK sampling time. The following endpoints will be determined:

<math>C_{max}</math>, <math>t_{max}</math>, and <math>AUC_{0-24}</math> during the first dosing interval on Day 1,

<math>C_{max}</math>, <math>t_{max}</math>, and <math>AUC_{\tau}</math> during a dosing interval at steady state (i.e., at Month 2),

AI between Day 1 and Month 2.

To evaluate the PD of cenerimod 4 mg in Chinese participants.	
PD endpoints
 

Change in total blood lymphocyte count from baseline to each post-baseline assessment.

Objectives	Endpoints

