#### **7.2.2.2 *British Isles Lupus Assessment Group***

The BILAG will be assessed by the investigator or delegate as per the schedule of assessments [see Section 1.3].

The scoring system for the BILAG index of disease activity is based upon the principle of the physician's intention to treat, and the main feature of the BILAG index is that disease activity in different organs/systems is reported separately. The investigator will record clinical features covered by the BILAG index of lupus disease activity and relevant data will be recorded in the BILAG form. There are 9 systems: constitutional, mucocutaneous, neuropsychiatric, musculoskeletal, cardiorespiratory, gastrointestinal, ophthalmic, renal, and hematological. Immunological data do not contribute to BILAG scores, but basic hematology and assessment of renal function determine the scores of the relevant systems [see Appendix 7]. As cenerimod causes a reduction in the peripheral blood lymphocyte count, and hence the complete WBC count, these data will not contribute to the scoring.

A score is calculated for each system depending on the clinical features present and whether they are "not present", "new", "worse", "the same" or "improving" in the last 4 weeks compared to previous assessment. Of note, the "improving" score MUST respect the following definition:

- The amount of improvement is sufficient for consideration of reduction in therapy and would not justify escalation in therapy,  
*and*
- Improvement must be **present currently and for at least 2 weeks** out of the last 4 weeks,  
*or*
- The manifestation has **completely resolved and remained absent over the whole last 1 week**.

The scoring categorizes disease activity into 5 different grades from A to E:

- Grade A represents very active disease requiring a prednisone dose of > 20 mg/day or equivalent and/or immunosuppressive drugs.
- Grade B represents moderate disease activity requiring a prednisone dose of < 20 mg/day or equivalent, topical steroids, topical immunosuppressives, antimalarials, or NSAIDs.
- Grade C represents mild stable disease.
- Grade D represents no current disease activity, but the system has been previously affected.
- Grade E represents no current or previous disease activity.

Important extensions of selected BILAG glossary and SLEDAI-2K clinical variable definitions are detailed below. Of note, protocol-specific extensions for BILAG are highlighted in italic below:

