### ***Laboratory data***

Observed and change from baseline laboratory variables for hematology, blood chemistry, and urinalysis for all scheduled post-baseline visits will be summarized. The number (%) of participants with a marked laboratory abnormality (see Appendix 13) will be tabulated.

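### The eosinophil cell in Appendix 13 joins two limits that lie 10- to 50-fold apart, so the marked flag rests on a percentage that the intended lymphocyte effect can raise

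*Combined protocol and SAP*

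**What the plan says.** The Appendix 13 table gives total eosinophils a single graded level. HH is "> 5.0 × 10 e9/L or > 5" per cent, with a bracketed conversion to cells/mm³ that restates only the absolute limit. LL, LLL and HHH are not defined, and the row carries no ALERT.

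The introduction to that table defines a marked abnormality "with grading of abnormalities at two levels: LL/HH and LLL/HHH", so HH is marked. It adds that, in specific cases, thresholds "are adjusted based on the known PD effect of the study treatments", and it names lymphocytes as the example.

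Section 9.2.1 (Laboratory data) states: "The number (%) of participants with a marked laboratory abnormality (see Appendix 13) will be tabulated". Table 5 lists "Treatment-emergent marked laboratory abnormalities from baseline to all assessed time points" among the endpoints for safety and tolerability, which Section 3.1 makes a primary objective.

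The notes to Section 7.2.2.1 describe the fall in total WBC through lymphocytes as the main PD effect of the drug class, and drop leukopenia from the mSLEDAI-2K for that reason. Section 7.2.2.2 does the same for BILAG: "As cenerimod causes a reduction in the peripheral blood lymphocyte count, and hence the complete WBC count, these data will not contribute to the scoring".

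**The concern.** The cell has two faults.

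The first is internal and does not depend on the drug. An absolute count and a share are offered as alternatives, but they describe very different amounts of eosinophilia. With the word or between them, the lower one always governs.

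The second follows from the first. The governing limit is a share of total WBC, and the protocol expects cenerimod to reduce total WBC. A share can therefore rise after the first dose while the number of eosinophils stays the same. The protocol took this effect into account for two disease-activity scores and for the lymphocyte threshold, but shows nothing for this row.

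At stake is how one line of a primary-objective safety table is read. In a single-arm study of about 15 participants, each flag is 1/15, or about 7 percentage points. A reader who sees only the count of marked eosinophil values could take a denominator effect for an eosinophil response.

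**Working it through.** The plan gives no figure of its own to reproduce here. Section 9.4 states about 15 participants without a calculation.

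**Inputs from the documents.** The two eosinophil limits and the lymphocyte ALERT level of 0.2 × 10⁹/L come from Appendix 13. The lowest counts allowed at entry, WBC 2.0 and lymphocytes 0.5 × 10⁹/L, come from exclusion criterion 24.

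**Assumptions.** The eosinophil count is constant. Section 2.2 names natural killer cells and monocytes as unaffected and is silent on eosinophils. Baseline WBC, baseline lymphocytes and the size of the fall are also assumed, because the documents give no values.

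**Step 1: do the two limits agree?** They coincide where 0.05 × WBC = 5.0, that is at WBC = 5.0/0.05 = 100 × 10⁹/L. Below that, any count above 5.0 is also above 5%, so the absolute limit adds nothing.

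| WBC (×10⁹/L) | 5% of WBC | 5.0 ÷ that value |
|---|---|---|
| 2 | 0.10 | 50 |
| 4 | 0.20 | 25 |
| 5 | 0.25 | 20 |
| 8 | 0.40 | 12.5 |
| 10 | 0.50 | 10 |

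**Step 2: what does a lymphocyte fall do to the share?** Let W be baseline WBC and d the fall in lymphocytes. With eosinophils constant, the new share is the baseline share × W/(W − d). A participant crosses 5% if the baseline share exceeds 5% × (W − d)/W.

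| W | Lymphocytes | W − d | Factor | Baseline share that crosses |
|---|---|---|---|---|
| 2.0 | 0.5 to 0.2 | 1.7 | 1.18 | > 4.25% |
| 5.0 | 1.2 to 0.5 | 4.3 | 1.16 | > 4.30% |
| 5.0 | 1.5 to 0.5 | 4.0 | 1.25 | > 4.00% |
| 6.0 | 2.0 to 0.5 | 4.5 | 1.33 | > 3.75% |
| 8.0 | 1.0 to 0.5 | 7.5 | 1.07 | > 4.69% |

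The first row uses the entry minima and the ALERT level; pairing them is a scenario, not a prediction. In all rows the affected band runs from the cut up to 5%, so it is 0.31 to 1.25 percentage points wide. The absolute eosinophil count at the cut (cut × W) runs from 0.085 to 0.375 × 10⁹/L, which is 59 to 13 times below 5.0.

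**Step 3: how likely is at least one such flag among 15?** The chance is 1 − (1 − p)¹⁵, where p is the proportion of participants who lie in the band and cross. The documents do not give p. For assumed values of 2%, 5%, 10% and 20%, the chance is 26%, 54%, 79% and 96%.

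**Step 4: does another row share the feature?** The polymorphonuclear/band-cell row has HH above 90% and HHH above 95%. With WBC 8.0, lymphocytes falling from 0.8 to 0.2 and a baseline share of 84% (all assumed), the share becomes 84% × 8.0/7.4 = 90.8%, which crosses HH. Two other assumed cases, starting at 68% and 64%, reach only 82.9% and 84.2%.

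**The case against.** A reader might infer that the safety table will report marked eosinophilia caused by the drug's intended effect. The documents do not support that. They do not say that eosinophils stay constant, and they give neither the size of the lymphocyte fall nor any baseline eosinophil share. Only a participant already close to 5% crosses through the denominator alone. The supported word is can.

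A reader might also infer that, without a control arm, the artefact could not be recognised. That does not follow. Appendix 1 includes a leukocyte count with differential, Section 9.2.1 summarises observed values and changes from baseline by visit, and Section 9.2.3 lists lymphocyte counts by participant. The absolute count separates a true rise from a smaller denominator. What remains is that the marked-abnormality table does not itself make this visible.

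It is fair to add that Appendix 13 promises adjustment only in specific cases, so no commitment is broken. The mSLEDAI-2K and BILAG exclusions concern disease scores, not laboratory flags. Section 9.2.1 also leaves the analysis of marked abnormalities to the SAP. The deferral helps only in part, because the thresholds are fixed in Appendix 13 for standardised reporting and Section 9.2.1 cites that appendix directly.

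The objection to simply deleting the percentage also stands. A count above 5.0 × 10⁹/L is impossible at a WBC of 5.0 × 10⁹/L or below, and at WBC 10 it needs a share above 50%. With HHH undefined, deletion would nearly disable the only marked eosinophil criterion, and nothing in the documents supports keeping that limit over the other.

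**Conclusion.** The concern holds as a minor point. The conflict between the limits is plain arithmetic and needs no assumption about cenerimod: the flag can label as marked a count 10 to 50 times below the cell's own absolute limit at WBC 10 to 2 × 10⁹/L.

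The PD effect is conditional. Over the assumed blood counts, a constant eosinophil count gives a share inflated 1.07- to 1.33-fold, and baseline shares above a cut of about 3.8% to 4.7% can cross 5%. Whether any of about 15 participants falls in that band cannot be determined from the documents. Flags could also come from ordinary variation around a low limit.

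The severity is limited because Appendix 13 attaches no ALERT to this row and the absolute data will be available.

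**What to change.** 1. The sponsor should reconcile the two limits in the Appendix 13 eosinophil cell and state how they relate. This review does not choose the threshold. The same 5% cut appears as eosinophilia in the Figure 3 footnote (Section 5.8.1.7) and should be considered at the same time.
2. In the marked-abnormality table (Section 9.2.1 and the SAP), report participants who meet the absolute limit separately from those who meet only the percentage. Beside the percentage-only flags, show the absolute eosinophil count and its change from baseline.
3. Apply the same caution to the polymorphonuclear/band-cell row, which is also a percentage.

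The table changes cost one or two extra rows from data already collected. Reconciling the limits means a wording change in Appendix 13 and a check that the matching laboratory flag follows it.
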